PROTOCOL ADDENDUM

A Comparison of External Ventricular Drain Catheter Diameter on Occlusion and Replacement: A Multicenter Randomized Trial

Primary Investigator: [name]
Sub-investigator: [name]
[name] BSN, CCRC
[name] BSN

Background and Purpose:

[figure not shown]
Ventriculostomy is a common neurosurgical procedure. A Nationwide Inpatient Sample (NIS) database study demonstrated a significant increase in ventriculostomy utilization from 1988-2010, with over 35,000 hospitalizations including a procedural code for ventriculostomy in 2010¹.

Ventriculostomy occlusion is a common complication after external ventricular drain (EVD) placement. A review of published prospective and retrospective studies indicates that approximately 1-7% of EVDs require replacement secondary to occlusion²⁻⁸. Furthermore, in the NIS database study of over 101,000 hospitalizations in which ventriculostomy was performed, nearly 6% of patients required at least one additional ventriculostomy procedure¹. Studies have demonstrated non-patent EVD in 19-47% of patients⁸⁻¹⁰, however these studies did not prospectively evaluate EVD occlusion as a primary endpoint, report on number of catheter irrigations performed, or identify risk factors for EVD occlusion.

Recently, we completed a retrospective review of a prospectively collected database of patients undergoing bedside EVD placement with the primary outcome of interest being catheter occlusion (published in *Journal of Neurosurgery*). This sample included 101 patients over a 1 year period. Two Codman (Codman & Shurtleff Inc., Raynham, MA) catheters were available for use (Clear Bactiseal 'large' catheter: outer diameter 3.4 mm, inner diameter 1.9 mm; and Orange Bactiseal 'small' catheter: outer diameter 3 mm, inner diameter 1.5 mm). The decision regarding which catheter to use was made at the time of the procedure based on resident preference and availability. Both temporary occlusion (requiring flushing but patency could be restored) and permanent catheter occlusion (requiring replacement) were common, occurring in 41% and 19% of patients, respectively. Over 25% of small catheters became occluded during the study period compared to 11% of large catheters. Small catheters were associated with a 3.4 times greater odds of occlusion than the larger diameter catheters on multivariable regression analysis (P= 0.04; Figure 1). This study suggests that the preferential use of larger diameter catheters may reduce the risk of ventriculostomy occlusion and need for replacement, however the study was not randomized and catheter selection may have been biased.

Recently, a smaller retrospective study of patients with intraventricular hemorrhage performed by Gilard and colleagues demonstrated a lower rate of occlusion and no increased risk of hemorrhage with larger bore catheters¹¹. Otherwise, there is no data in the literature supporting the preferential use of catheters based on size (clinical equipoise). Therefore, a randomized trial comparing small versus large catheters in terms of occlusion and need for replacement will be beneficial in confirming differential occlusion risk based on catheter size.

Figure 1: Kaplan-Meier curve demonstrating catheter survival for large and small catheters.

References

Wake Forest University, site PI: [name] MPH

Mount Sinai Hospital, New York, NY; site PI: [name]

Treatment Arms

Patients will be randomized 1:1 to receive either a small (ID 1.5 mm) antibiotic impregnated catheter or a large (ID 1.9 mm) antibiotic impregnated catheter.

Study Population

Detailed inclusion and exclusion criteria are shown in Table 1. All adult patients with spontaneous intracranial hemorrhage requiring placement of a frontal external ventricular drain at a study center will be potential candidates for inclusion. Patients may undergo placement of the EVD either at the bedside or in the operating room or angiography suite. Patient (if able to consent) or next of kin must be immediately available in person or by phone, if approved procedure for individual center's IRB, to consent for randomization for the patient to be included in the study.

Based on occlusion data from the previously referenced prospective study, as well as a P-value of 0.05 and power of 0.80, the study will need to include 90 patients to demonstrate statistical significance. To ensure that power is adequate, we will plan to enroll 120 patients (60 in each arm).

Randomization

Randomization will be performed through the use of real-time, internet-based randomization procedure contained within RedCap to achieve a distribution balance for age, sex, diagnosis, and intraventricular hemorrhage distribution.

Primary Outcome Measure

The primary outcome measure will be permanent catheter occlusion, defined by a non-functioning (non-patent) EVD where patency cannot be restored through catheter manipulation or flushing.

Table 1: Inclusion and exclusion criteria.

Inclusion Criteria	Exclusion criteria
Adult patient (18-85 years) requiring frontal EVD placement	Patient cannot consent and next of kin cannot provide consent prior to procedure
Diagnosis of spontaneous subarachnoid hemorrhage, intraventricular hemorrhage, intraparenchymal (or cerebellar) hemorrhage due to aneurysm, vascular malformation (arteriovenous malformation or arteriovenous fistula), hypertension, or idiopathic etiology	Diagnosis of traumatic brain injury (EVD often times remain clamped for prolonged periods)
Attending neurosurgeon decides that frontal EVD indicated for patient treatment with planned CSF drainage for 72 hours or more	Anticoagulated prior to admission and not fully reversed with Coumadin (warfarin), Effient, Plavix, therapeutic heparin infusion, therapeutic subcutaneous Lovenox, therapeutic subcutaneous Arixtra, or other therapeutic anticoagulant or antiplatelet agent (ASA not included)
Glasgow Coma Score of 5 or higher within 12 hours of EVD insertion	Best Glasgow Coma Scale of 4 or less within 12 hours of EVD insertion
	Hunt and Hess subarachnoid hemorrhage grade of 5
	Age 86 or greater
	Plan for placement of EVD through non-frontal burr hole approach

Secondary Outcome Measures

1. Catheter replacement: defined by replacement of the ipsilateral EVD due to permanent occlusion, or placement of a contralateral EVD in the setting of a non-functioning ipsilateral catheter. Catheters placed contralaterally in the setting of a functioning ipsilateral catheter will not be considered replacements.
2. Temporary occlusion: defined by non-functioning (non-patent) catheter requiring neurosurgeon flushing or manipulation in order to restore patency. By definition, such maneuvers must restore patency of the EVD such that it is functioning normally afterwards. Multiple temporary occlusions may be possible.
3. Procedure-related hemorrhage: Presence of new catheter-related intraparenchymal hemorrhage, subdural hematoma, or intraventricular hemorrhage on CT scan after placement.
4. Symptomatic hemorrhage: Presence of new neurologic deficits as a result of EVD-related hemorrhage, or resulting in need for further procedures due to new EVD-related hemorrhage (craniotomy for hematoma evacuation, ICP monitoring, etc).
5. Administration of intraventricular tPA (Tissue Plasminogen Activator) regardless if catheter patency is restored.

Protocol

Once EVD is deemed indicated by the attending neurosurgeon, the patient becomes a candidate for enrollment. At this point, research staff will determine candidacy by reviewing inclusion and exclusion criteria. Patients that meet inclusion criteria, in the absence of exclusion criteria, will be consented and randomized by enrolling the patient in RedCap. Patients who meet inclusion criteria and have no exclusion criteria but cannot be consented before treatment will undergo placement of an EVD, with catheter size based on surgeon preference, and will be enrolled in an ongoing prospective database.

Procedural technique

All EVD will be placed by neurological surgeons in either the major operating suite or in an ICU setting using a previously published protocol¹². This protocol includes using a burr hole entry point 1 cm anterior to the coronal suture in the mid-pupillary line, prep and sterile drape, pre-procedural antibiotic administration, and tunneling the catheter to an exit site at least 5 cm from the incision. Following EVD insertion, physicians will document procedural factors on the procedural data sheet (Appendix A)

Flushing technique

No formal published protocols exist for catheter irrigation. In general, physicians are instructed to first attempt distal irrigation of the drainage chamber using sterile techniques (rarely effective), followed by gentle aspiration of the proximal system and catheter if distal flushing is not effective. If these do not restore patency, a small volume of sterile saline, 3 ml or less, is flushed proximally into the catheter. Patency is checked by lowering the EVD drainage system and evaluating for spontaneous flow through the EVD. Each irrigation will be recorded on the daily record sheet (Appendix B).

Treatment Arms

Enrolled patients will be randomized to one of two catheters in a 1:1 randomization scheme. These include the antibiotic-impregnated 'large' catheter (outer diameter 3.4 mm, inner diameter 1.9 mm) and an antibiotic-impregnated 'small' catheter (outer diameter 3 mm, inner diameter 1.5 mm). After placement of the EVD catheter, all clinical and radiographic follow-up will be the same for both treatment arms.

Data collection

Data will be collected prospectively by the research team. Trial data will be reported via RedCap. Collected data will include a number of factors, such as: age, gender and underlying diagnosis; procedural data including faculty versus resident physician as primary proceduralist, number of passes, side of placement; radiographic data including ventricular size (based upon Evan's ratio: maximum bifrontal ventricular distance divided by maximal intracranial biparietal distance), pre-procedural midline shift, presence of intraventricular hemorrhage, catheter location, and presence of catheter-related hemorrhage; and clinical data including symptomatic hemorrhage, number and type of catheter irrigations, catheter

occlusion and replacement, number of catheter days, catheter endpoint, cerebrospinal fluid analysis and incidence of catheter-related infection (Appendices).

Imaging Review

A blinded physician at each treatment center will review brain imaging to document all radiographic data into RedCap, including: Evan's ratio, midline shift, presence of intraventricular hemorrhage, catheter location, and presence of catheter-related hemorrhage. At time of site activation for each center, the radiographic reviewer will undergo a training session via conference call, performed by the study PI (KF), which will ensure consistent interpretation of imaging across centers. The primary center may ask for select image series to be uploaded into RedCap for review by the PI.

Study Endpoint

Patients will have met the study endpoint when the EVD is intentionally removed by the supervising physician, in any of the following scenarios: 1) The EVD is removed due to resolution of hydrocephalus; 2) The EVD is removed because it is non-functional but not replaced; 3) The EVD is removed and is replaced with a shunt. Once the endpoint has been reached, no further data collection will occur for that study subject.

Adverse Events

Adverse events will be recorded. Adverse events include: symptomatic intracranial intraparenchymal or subdural hemorrhage (with new neurologic deficit or need for surgery), symptomatic intraventricular hemorrhage (defined as new neurologic deficit, need for surgery, or catheter occlusion within 2 hours of placement requiring contralateral EVD placement), meningitis (confirmed by positive CSF cultures and initiation of antibiotic therapy), catheter in extraventricular position on placement, and catheter malposition after confirmation of correct positioning requiring replacement (ie. catheter is unintentionally pulled out by nurse, patient, or due to loose sutures).

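### The stated 90 patients for 80% power does not follow from the occlusion rates the protocol prints; those rates need about 140 to 236 (two-sided), and 120 gives about 51% to 74% power

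*Protocol*

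**What the plan says.** The sample size paragraph under Study Population names its source as "Based on occlusion data from the previously referenced prospective study". It gives the error rates and the resulting size together: "a P-value of 0.05 and power of 0.80, the study will need to include 90 patients to demonstrate statistical significance". The planned enrolment is then set higher: "To ensure that power is adequate, we will plan to enroll 120 patients (60 in each arm"). The paragraph gives no assumed event rates, test, sidedness or dropout allowance.

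The source can only be the investigators' own series of 101 patients in Background and Purpose, introduced as "Recently, we completed a retrospective review of a prospectively collected database of patients undergoing bedside EVD placement". That section reports temporary and "permanent catheter occlusion (requiring replacement) were common, occurring in 41% and 19% of patients, respectively". By catheter size it gives two results. The first is a pair of rates: "Over 25% of small catheters became occluded during the study period compared to 11% of large catheters". The second is an adjusted effect estimate from the same series: "Small catheters were associated with a 3.4 times greater odds of occlusion than the larger diameter catheters on multivariable regression analysis".

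The 19% for permanent occlusion lies between the two rates by size and the 41% for temporary occlusion does not. The two rates are therefore those of permanent occlusion, which is the trial's primary outcome. The other occlusion rates quoted from the literature are not split by catheter size.

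**The concern.** This is the trial's only sample size justification, and it serves the single primary outcome. It presents 90 as sufficient and the further 30 patients as a safety margin. A difference of roughly 25% to 30% against 11% is hard to detect with 45 patients per arm, so the figure looked too small by inspection.

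If it is too small, the margin does not exist. The trial could then quite probably miss a difference of the size it was designed around, and a null result could be misread as evidence that catheter diameter does not matter.

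**Working it through.** **Inputs.** Large-catheter rate p2 = 0.11 (Background and Purpose). Small-catheter rate p1: printed only as above 25%, read here as 0.25 to 0.30. The upper end is supported by the printed odds ratio: odds 3.4 × 0.11/0.89 = 0.4202, so p1 = 0.4202/1.4202 = 0.296. Alpha 0.05, power 0.80 and 1:1 allocation are as stated. Test and sidedness are assumptions, so several were tried.

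**Two-proportion test, pooled variance.** With p̄ = (p1 + p2)/2,

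n per arm = [z_α √(2p̄(1−p̄)) + z_β √(p1(1−p1) + p2(1−p2))]² / (p1 − p2)²

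For 25% against 11%, two-sided: p̄ = 0.18; [1.960 × 0.5433 + 0.8416 × 0.5342]² / 0.14² = 1.5145² / 0.0196 = 117.03. That is 118 per arm, or 236 in total.

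Power = Φ{[(p1 − p2)√n − z_α √(2p̄(1−p̄))] / √(p1(1−p1) + p2(1−p2))}

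For the same rates and n = 60: Φ[(1.0844 − 1.0649)/0.5342] = Φ(0.0366) = 0.515. For n = 45: Φ[(0.9391 − 1.0649)/0.5342] = Φ(−0.235) = 0.407.

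| p1 vs 11% | Sides | n per arm | Total | Power at 90 | Power at 120 |
|---|---|---|---|---|---|
| 25% | 2 | 117.03 | 236 | 40.7% | 51.5% |
| 29.6% (OR 3.4) | 2 | 72.30 | 146 | 59.4% | 72.2% |
| 30% | 2 | 69.68 | 140 | 61.0% | 73.8% |
| 25% | 1 | 92.06 | 186 | 53.4% | 63.9% |
| 29.6% (OR 3.4) | 1 | 56.83 | 114 | 71.3% | 81.9% |
| 30% | 1 | 54.77 | 110 | 72.7% | 83.1% |

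A continuity correction raises the totals. Unpooled and arcsine versions lower them slightly, to no less than 106 (one-sided, 30%).

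**Log-rank test (Schoenfeld).** HR = ln(1−p1)/ln(1−p2); events = 4(z_α + z_β)²/(ln HR)²; patients = events / mean event rate.

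- 25%: HR 2.47. Two-sided, 38.45 events / 0.18 = about 214 patients (power 44% at 90, 56% at 120). One-sided, 30.28 events, about 168 patients (57%, 67%).
- 30%: HR 3.06. Two-sided, 25.09 events / 0.205 = about 123 patients (67%, 79%). One-sided, 19.76 events, about 97 patients (78%, 87%).

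**What would give 90.** Holding 11% for large catheters, 80% power with 90 patients requires these small-catheter rates:

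| Test | Small-catheter rate | Implied odds ratio |
|---|---|---|
| Log-rank, one-sided | 30.7% | 3.6 |
| Two-proportion, one-sided | 32.3% | 3.9 |
| Log-rank, two-sided | 33.5% | 4.1 |
| Two-proportion, two-sided | 35.7% | 4.5 |

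All four odds ratios exceed the printed 3.4.

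**Check against the source counts.** Assume one catheter per patient, 19 occlusions in 101 patients, and a large-catheter rate that rounds to 11%. The splits with a crude odds ratio of 3.3 to 3.5 are 12/40 vs 7/61, 13/45 vs 6/56 and 12/39 vs 7/62. Two-sided they need 150, 150 and 136 patients, with 71% to 75% power at 120.

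**A possible origin.** At 27.5% against 11%, two-sided, the formula gives 88.44, so 89 per arm. A per-arm number may have been taken as a total; the document cannot confirm this.

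**The case against.** The strongest reply is that the true inputs are not printed. The small-catheter rate has no stated upper limit, the Kaplan-Meier figure and the published study are not visible here, and the 30% ceiling used above is an assumption. Some inputs consistent with the printed totals do give about 90:

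- A split of 12/37 vs 7/64 (32.4% vs 10.9%) needs exactly 90 one-sided, though 114 two-sided.
- A split of 11/30 vs 8/71 (36.7% vs 11.3%) needs 88 two-sided.
- Reading 3.4 as a hazard ratio needs 16.51 events one-sided (16.51/0.19 = about 87 patients) or 20.96 two-sided (20.96/0.23 = about 91).

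The first two imply crude odds ratios of 3.9 and 4.6. The printed 3.4 is adjusted, so the crude value need not match it. It is also fair that exactly 25% is a boundary: the lowest split consistent with the printed figures is 14/55 vs 5/46 (25.5%), which needs 218 and gives 54.5% power at 120. Finally, the choice of test is often left to the statistical analysis plan.

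Much of this stands as a limit on certainty. It shows that 90 could have come from inputs the protocol does not state. It does not make 90 follow from those it does. A rate near 36% would not ordinarily be described as just above 25%, the protocol prints 3.4 as an odds ratio, and it states neither a one-sided test nor a time-to-event primary outcome. Nor is the complaint that a test is unnamed: the protocol commits itself to a number and to a claim of adequate power.

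**Conclusion.** The point holds. Across 25% to 30% against 11%, power with 90 patients is 41% to 78% over the four tests tried, so the stated 80% is never reached.

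Under the conventional two-sided two-proportion test, 90 patients would miss such a difference with probability 39% to 59%, and 120 patients with probability 26% to 49%. The best single reading, from the printed odds ratio, is 146 patients needed and 72% power at 120.

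Whether 120 suffices depends on the unstated choices. It reaches 80% power from these small-catheter rates against 11%:

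- two-proportion test: about 32% two-sided, 29% one-sided;
- log-rank test: about 30% two-sided, 28% one-sided.

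The exact shortfall therefore rests on the assumed small-catheter rate, test and sidedness. That 90 does not follow from the printed rates, read as 25% to 30% against 11%, does not depend on which of these tests was meant.

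**What to change.** In the sample size paragraph:

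- State the assumed occlusion rate in each arm and its source, the test, and the sidedness. If Kaplan-Meier estimates or other rates from the earlier study were used, print them.
- Replace 90 with the number those inputs give. Two-sided examples: 236 for 25% vs 11%, or 146 for 29.6% vs 11%.
- Report the power at the planned 60 per arm (about 51% to 74% for 25% to 30% vs 11%, two-sided) and the difference detectable with 80% power (about 32% vs 11%, two-sided).
- Remove the statement that 120 ensures adequate power unless the stated inputs support it.

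The correction is wording only and needs no added enrolment. Its cost is a less favourable stated power, which may prompt questions about the trial's size. If the investigators prefer to secure 80% power two-sided, the addition to 120 runs from 26 patients (146 − 120, at 29.6% vs 11%) to 116 (236 − 120, at 25% vs 11%).

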APPENDIX B:

STUDY SUBJECT DAILY RECORD SHEET

Subject No: _____

Date: _____

Side (Circle one): R L

At time 00:00, EVD is (Circle one): Clamped Open to Drain

At time 00:00, Height of EVD (cm of water): _____

RECORD ANY EVD HEIGHT OR CLAMPING ORDER CHANGES:

Height Change #1: Changed to: _____ cm water Time:

Height Change #2: Changed to: _____ cm water Time:

Height Change #3: Changed to: _____ cm water Time:

Clamping/Unclamping #1: Clamped Unclamped Time:

Clamping/Unclamping #2: Clamped Unclamped Time:

Clamping/Unclamping #3: Clamped Unclamped Time:

RECORD ANY EVD FLUSHING EVENTS:

1. Time:	 Distal system flushed only	 Proximal system aspirated only
	 Proximal system flushed - number of times: _____	
	RESULT:  EVD functioning  EVD occluded	
2. Time:	 Distal system flushed only	 Proximal system aspirated only
	 Proximal system flushed - number of times: _____	
	RESULT:  EVD functioning  EVD occluded	
3. Time:	 Distal system flushed only	 Proximal system aspirated only
	 Proximal system flushed - number of times: _____	
	RESULT:  EVD functioning  EVD occluded	
4. Time:	 Distal system flushed only	 Proximal system aspirated only
	 Proximal system flushed - number of times: _____	
	RESULT:  EVD functioning  EVD occluded	
5. Time:	 Distal system flushed only	 Proximal system aspirated only
	 Proximal system flushed - number of times: _____	
	RESULT:  EVD functioning  EVD occluded	

6. Time:	 Distal system flushed only	 Proximal system aspirated only
	 Proximal system flushed - number of times: _____	
	RESULT:  EVD functioning  EVD occluded	
7. Time:	 Distal system flushed only	 Proximal system aspirated only
	 Proximal system flushed - number of times: _____	

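### Does the unmasked bedside split between permanent and temporary occlusion need a change to the primary outcome or its records?

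*Protocol*

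**What the plan says.** Under Primary Outcome Measure, an EVD is permanently occluded when it is non-functioning and "patency cannot be restored through catheter manipulation or flushing". Under Secondary Outcome Measures, temporary occlusion is the same non-patent state "requiring neurosurgeon flushing or manipulation in order to restore patency", with success required.

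The Flushing technique section begins "No formal published protocols exist for catheter irrigation. In general, physicians are instructed to first attempt distal irrigation". It then gives an order (distal irrigation, proximal aspiration, a small proximal saline flush) and a patency test: lower the drainage system and look for spontaneous flow. It sends each irrigation to the daily record sheet.

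That sheet, Appendix B, is headed "RECORD ANY EVD FLUSHING EVENTS". It has boxes for distal flush and proximal aspiration, an entry "Proximal system flushed - number of times", and a result of functioning or occluded for each of up to 15 events.

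The only blinded role is in Imaging Review: "A blinded physician at each treatment center will review brain imaging to document all radiographic data into RedCap". Occlusion is not among its listed items. Study Endpoint includes the case "The EVD is removed because it is non-functional but not replaced". The second Treatment Arms section states that clinical and radiographic follow-up after placement is the same in both arms.

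**The concern.** The two outcomes start from one bedside finding and part according to whether an attempt to clear the catheter succeeds. Success depends partly on how long the physician persists, and the protocol sets no point at which attempts count as failed. The catheters differ in outer diameter (3.4 mm and 3 mm), no masking of the physicians is described, and the Background reports the team's own result in favour of the large catheter.

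Less effort on one size would turn its temporary occlusions into permanent ones; more effort would do the reverse. The first could create a false difference and the second could hide a true one. Two features seem to leave this unguarded: the protocol does not say that the Appendix B log decides the primary outcome, and the sheet has no entry labelled manipulation although both definitions use the word.

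**Working it through.** **Coverage of the form.** The maneuvers named in Flushing technique, set against Appendix B:

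| Maneuver named in the protocol | Entry in Appendix B |
|---|---|
| Distal irrigation | Box for distal flush |
| Proximal aspiration | Box for proximal aspiration |
| Proximal saline flush | Box with a count |
| Flow check afterwards | Result: functioning or occluded |

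Every named maneuver has an entry. Aspiration is not flushing, so it is a natural reading of manipulation. The protocol names no further patency maneuver that the form omits. Data collection also lists the number and type of irrigations, catheter occlusion and replacement, and catheter endpoint as trial data. A permanent declaration can therefore be compared with the flush log and with what happened to the catheter.

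**Size of the possible distortion.** The protocol gives no figure for differential effort, so the shifts below are assumptions. It also names no test and no sidedness; I use two-sided 5% tests.

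Inputs:
- 60 patients per arm (Study Population).
- Occlusion of 25% with small catheters (stated as over 25%) and 11% with large ones (Background).
- Null base rates of 11% and (25% + 11%)/2 = 18%.
- Expected permanent events: 0.11 × 120 = 13.2 to 0.19 × 120 = 22.8, where 19% is the permanent-occlusion rate in the earlier series.

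Method: sum P(X = i) × P(Y = j) over all pairs (i, j) that the test rejects, where X and Y are binomial with n = 60.

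(a) No true difference; small-arm events moved up from temporary to permanent. Ranges cover the two base rates.

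| Shift | Chi-square error | Fisher error |
|---|---|---|
| None | 4.8-5.0% | 2.3-2.8% |
| One patient (1/60 = 1.7 points) | 5.5-5.8% | 3.0-3.2% |
| 3 points | 6.9-7.5% | 4.2-4.3% |
| 6 points | 12.8-14.9% | 8.4-10.0% |

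At 6 points the moved events are 0.06/0.24 = 25% to 0.06/0.17 = 35% of all small-arm permanent events. Small-arm events moved down by one patient give a chi-square error of 5.4-6.0%, and by 3 points 6.9-8.6%.

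(b) True rates 25% and 11%; small-arm events moved down from permanent to temporary.

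| Shift | Chi-square power | Fisher power |
|---|---|---|
| None | 52% | 42% |
| One patient | 43% | 34% |
| 3 points | 36% | 28% |
| 6 points | 22% | 16% |

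Power is only 52% before any shift. That shortfall is a matter of sample size and would remain if every event were classified perfectly.

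**What the possible remedies would achieve.**
- Reporting logged attempts by arm is ordinary SAP content, and the SAP was not available. It would also be hard to read: catheter diameter may itself affect how readily an obstruction clears, so a difference in attempts need not be bias.
- A sensitivity analysis limited to events with a documented failed proximal flush selects on the same unmasked effort. It could drop true permanent occlusions unequally by arm.
- A blinded check of the sheets for permanent declarations would test consistency only. The result box is completed at the bedside, and such a check never sees events that were moved from permanent to temporary.

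None of these removes differential effort or changes the primary count.

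**The case for a change.** The strongest case for acting is that the record form is fixed in the protocol, and a later SAP cannot recover attempts that were never written down. In the earlier series temporary occlusion occurred in 41% of patients and permanent occlusion in 19%, so the pool next to the boundary is about twice the size of the primary pool (41/19 = 2.2). With 13 to 23 events expected, one or two classifications matter, as table (b) shows. An occluded tick on a sheet that allows 15 events does not by itself separate a permanent occlusion from a failed attempt that is later reversed. Replacement and non-functional removal are partial corroboration only, because they follow the same clinicians' decisions.

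All of this is accurate as description, and the limitation stands: the judgement is made at the bedside without described masking, and manipulation is undefined. What does not follow is a change. That some maneuver goes unlogged is inferred from one undefined word. Masking the operators is hardly feasible when the devices differ visibly in size. Occlusion is collected in its own right, so the primary outcome does not rest on a single tick. The commitment to equal follow-up does not enforce equal effort, but it is the protocol's stated position and nothing in the text contradicts it.

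**Conclusion.** No change to the plan is needed. This is a limitation common to device trials with unmasked operators, together with a small gap in wording. It is not a contradiction or a wrong figure. For a one-patient upward shift under the null the effect is slight: chi-square error 5.5-5.8%, Fisher at or below 3.2%. Error rates of 8-15% require 25-35% of small-arm permanent events to be misplaced, which nothing in the protocol supports. The power loss in (b) is larger per patient, but it too rests on an assumed shift and direction.

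The conclusion assumes that manipulation means the aspiration and flushing already on the form, and that the separately collected occlusion item is the source of the primary outcome. Both are sensible readings that the study team can confirm in its data-handling instructions, with no effect on the definition or the count. It would be different if the protocol named a patency maneuver that the form could not record, or gave evidence that effort differed by catheter size. It does neither.

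### Does the study-endpoint rule fail because it lists no scenario for an EVD replaced by another EVD or pulled out by accident?

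*Protocol*

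**What the plan says.** The Protocol, Study Endpoint, states: "Patients will have met the study endpoint when the EVD is intentionally removed by the supervising physician, in any of the following scenarios". The first scenario is resolved hydrocephalus; the other two are "2) The EVD is removed because it is non-functional but not replaced; 3) The EVD is removed and is replaced with a shunt". The section closes: "Once the endpoint has been reached, no further data collection will occur for that study subject".

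Other sections foresee removals or second drains that are not in that list:

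- Secondary Outcome Measures, item 1: "Catheter replacement: defined by replacement of the ipsilateral EVD due to permanent occlusion, or placement of a contralateral EVD" when the first drain no longer works. The item adds: "Catheters placed contralaterally in the setting of a functioning ipsilateral catheter will not be considered replacements".
- Adverse Events: "catheter malposition after confirmation of correct positioning requiring replacement", with accidental pulling-out as the example.
- Background and Purpose, on the earlier series of 101 patients, where temporary occlusion is named first and permanent occlusion second: "permanent catheter occlusion (requiring replacement) were common, occurring in 41% and 19% of patients, respectively".

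On recording, Procedural technique says: "Following EVD insertion, physicians will document procedural factors on the procedural data sheet (Appendix A"). Flushing technique sends each irrigation to the daily sheet, Appendix B. Both sheets have a date and a side; neither has a catheter size or a catheter number. Data collection says that trial data are reported through RedCap and gives an open-ended list of items. Both Treatment Arms sections allocate the patient to one of two catheter sizes and do not mention the size of a replacement.

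**The concern.** Taken literally, an EVD exchanged for another EVD meets none of the three scenarios, and an accidental removal fails the condition that removal be intentional. Both are foreseen elsewhere in the Protocol. Collection then continues while a catheter of unspecified size is in place, and the primary outcome and temporary occlusion are not expressly limited to the first catheter.

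Three consequences could follow:

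- **Different follow-up between sites.** One site might stop at the first exchange and another at the last removal.
- **Unequal exposure between arms.** If small catheters occlude more often, more small-arm patients have a second catheter on which temporary occlusions, hemorrhage or tPA use can accrue.
- **Two drains at once.** If a contralateral EVD goes in while the first still works, it is not a replacement. When the first later occludes and is removed, the second scenario is literally met with a drain still in place. If the contralateral EVD goes in after the first has failed, it is a replacement and collection continues.

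**Working it through.** **1. Each route against the rule**

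| Route | Listed? | Patient's state afterwards | Natural reading |
|---|---|---|---|
| Hydrocephalus resolved | Yes, scenario 1 | No EVD | Collection ends |
| Non-functional, not replaced | Yes, scenario 2 | No EVD | Collection ends |
| Shunt placed | Yes, scenario 3 | No EVD | Collection ends |
| Replaced by another EVD | No | EVD in place | Collection continues |
| Pulled out, replaced | No | EVD in place | Collection continues |
| Pulled out, not replaced | No | No EVD | No scenario fits; no drain left to observe |

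The three listed routes are the ways a patient becomes free of an EVD. Scenario 2 sets replaced drains aside in so many words, and both the opening and closing sentences of the section speak of the patient, not the catheter. The only true omission is a drain pulled out and not replaced.

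**2. Can first and later catheters be told apart?** An insertion sheet is completed after EVD insertion and carries a date. The daily sheet carries a date and a time for each flush. A second insertion date therefore divides events into before and after, with doubt confined mainly to the day of exchange. Analyses to final removal and analyses cut at the first exchange are both possible.

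**3. Are Appendices A and B the whole record?** No. Infection, catheter days and catheter endpoint are in the data list, and intraventricular tPA is a secondary outcome, yet none has a field on either sheet. They must be captured in RedCap, whose forms are not shown. Whether size is captured there cannot be known.

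**4. How many patients take the unlisted route?** Inputs are 60 per arm (Study Population), and 19% overall, 25% small and 11% large (Background and Purpose; the small-catheter figure is given as over 25%).

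- Overall: 120 × 0.19 = 22.8
- By size: 60 × 0.25 = 15 and 60 × 0.11 = 6.6; sum 21.6

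If 50% to 100% of these receive a new EVD (assumption), 7.5 to 15 small-arm and 3.3 to 6.6 large-arm patients have a later catheter. Insertions per patient are:

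- at 50%: 1 + 7.5/60 = 1.125 against 1 + 3.3/60 = 1.055; ratio 1.07
- at 100%: 1 + 15/60 = 1.25 against 1 + 6.6/60 = 1.11; ratio 1.13

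**5. Effect on temporary occlusion, per patient.** Assume that 41% of later catheters have one and that, independently, 41% of these patients already had one. Newly counted patients = number replaced × 0.41 × (1 − 0.41) = number replaced × 0.2419.

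- at 100%: 15 × 0.2419 = 3.63 and 6.6 × 0.2419 = 1.60, or 6.0 and 2.7 percentage points
- at 50%: 1.81 and 0.80, or 3.0 and 1.3 percentage points
- if all had already had one: 0 in both arms

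**6. Effect on the primary outcome, per patient.** A patient whose first catheter occluded permanently is already a case. Only a non-occlusive loss followed by a later occlusion adds one. With 2% to 10% of patients having such a loss (assumption; the Protocol gives no rate), the extremes are 60 × 0.02 × 0.11 = 0.13 and 60 × 0.10 × 0.25 = 1.5 events per arm.

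**The case for a change.** The strongest case for a change is that the end of follow-up is a protocol matter. An analysis plan cannot recover data that a site stopped collecting, and the omitted route is a secondary outcome in its own right. Later catheters would also be about 15/6.6 = 2.3 times as frequent in the small arm, so any ambiguity falls unevenly.

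Part of this stands. The Protocol implies follow-up to the last EVD without saying so. It is silent on the size of a replacement. It does not say which drain is meant when two are in place, and a drain pulled out and not replaced has no scenario.

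The consequences do not follow to the extent claimed. The uneven number of later catheters is itself a result of the allocated size, so counting their events per patient by allocated arm remains a valid randomized comparison. Size would matter only for an additional split by the catheter actually in place, and the visible forms do not show that such a split is impossible. The two-drain case is an edge case with no rate. It also needs the words about non-replacement in Study Endpoint to carry the technical definition from Secondary Outcome Measures, a link the Protocol does not make. Whether outcomes are counted on the first catheter or per patient is commonly left to the analysis plan, which is not shown.

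**Conclusion.** No change to the plan follows. The endpoint rule is loosely worded, but its coherent reading is collection until the patient's last EVD is out, and analysts can fill the remaining gap sensibly: compare patients by allocated size, and use the insertion dates where first-catheter events are wanted separately.

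The effect on the per-patient primary outcome is small, about 0.1 to 1.5 events per arm. The effect on per-patient temporary occlusion ranges from nothing to 6.0 against 2.7 percentage points, a gap of at most about 3.4 points before rounding. Multiple temporary occlusions, hemorrhage and tPA use can also accrue on later catheters; the documents give no rates to size these.

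These figures rest on the earlier series' rates carrying over, on 50% to 100% of permanent occlusions leading to a new EVD, on the independence assumption for temporary occlusion, and on the assumed 2% to 10% for non-occlusive replacement. The conclusion would weaken if sites in fact stopped collecting at the first exchange, but nothing in the text tells them to.
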